6.2.2 Secondary End-points

An analysis of the responses provided to the general questionnaire to be completed by both the clinician and the patient at each evaluation interval will be performed to describe various patient profiles and determine potential differences between subgroups of implanted recipients based on the implanted

device type and configuration. Furthermore the collated information from the Hearing summaries recorded at the baseline and annual intervals will be analyzed to provide further definition of the hearing loss configuration of the various patient profiles over time.

7 Subject Selection

7.1 Inclusion Criteria

- First time implantees, post-lingually deafened, awaiting first switch-on
(*i.e. registration date \geq implant date +120 days*)
- Device(s) implanted include one or more of implant devices from the company Cochlear.
- Configuration of implanted devices is either unilateral or bilateral at baseline registration
- Children 10 years or older and in accordance with local regulations and product labelling.
- Patient informed consent signed by the patient after or on the implant date (to be co-signed by their legal representative if under 18 years of age at time of registration)
- Mentally-able to complete self-assessment questionnaires
- Willingness to participate in the registry study for 2 years post-implant (and up to 3 years optionally).
- All implanted devices are routinely purchased under routine local conditions anticipated to be geographically stable.

NOTE: Unilateral device-users, electing to opt for a second sequential implant during the course of the 3 year post-implant follow-up period will be classified accordingly thereafter as sequential bilateral device users.

7.2 Exclusion Criteria

- Individuals excluded from participation in a registry according to national or local regulations.

8 Subject Identification and Confidentiality

In accordance with patient privacy laws, subjects will be identified anonymously on all evaluation forms and subsequently in the database only by a unique coded reference number that is automatically assigned by the database. This consists of the study number (assigned by Cochlear including the region managing the registry), country code, center code, and finally the patient specific code assigned in chronological order of implant at the clinic.

- Study number: Study specific **5277EU-**
- Country code: An abbreviation of the country name e.g. for Germany **GE**
- Center code: assigned by Cochlear for a specific clinic. e.g. clinic X in country Y - **02**
- Patient code: assigned automatically by the e-platform to indicate the chronological enrolment of patients at the clinic. E.g. the first patient enrolled is **-001**. No initials shall be included in the patient code which is centrally recorded. .

Example Patient Identifier code: 5277EU-GE-02-001

- The clinician will have the opportunity to include an identifier with 12 character spaces on the “*Clinician Baseline-Compulsory Form*” completed by the clinician. This will appear on the confidential patient listing for the clinic only.
- Should the patient move from the implant site where registered to another site any time after the registration for follow-up, the original clinic code defined by the system will be maintained.
- Clinicians will have the opportunity to transfer their registered implanted patient for follow-up via another participating site by completing the *Transfer patient form* online via the e-platform interface.

NOTE: Completed evaluation forms entered online or similar documents are confidential documents and will only be available to the Sponsor and their representatives, the clinic investigator, the investigational statistician, and if requested to the Ethics Committee. The name of any patient shall be kept confidential and shall not appear on any data forms, publication, or submission to regulatory authorities. Patients will be identified only by the subject code preserving anonymity.

9 Risk benefit analysis

9.1 Benefits

Patient benefits anticipated following implant treatment are listed in the accompanying product labelling issued with each market released Cochlear device.

9.2 Risks

Risks for the patient are listed in the product labelling accompanying each market released Cochlear device. There are no additional risks to the implanted patient deciding to participate in this observational study.

Investigators are informed during training on how to use the database and reminded of the compliance with data privacy for all patients on all communications externally and internally in relation to the study

10 Device Description

10.1 Investigation Product Description

All implanted recipients enrolled in the study will be implanted **with market released Cochlear products**. The accompanying product labelling for each device contains a description of the device and its intended use.

10.2 Investigational product traceability / recording

Registration cards for each implanted device are collected routinely for all implanted recipients receiving a market released **Cochlear** device and recorded through Cochlear’s post-market surveillance system following receipt from the clinic.

10.3 Handling and Reporting of Incidents

Report of any incident related to any device received by an implant recipient, shall follow the normal mandatory reporting procedures (according to latest MEDDEV guidelines) in place for all **market**

released Cochlear implant devices as implemented through Cochlear's complaints and issues handling procedure for routine post market surveillance. The schedule for the initial reporting of an incident or near incident commences from when Cochlear is informed in accordance with Cochlear's complaints and issues handling procedure for all marketed released products.

10.4 End of study OR Early termination or withdrawal

Following registration of the implanted recipient at baseline, the registered patient may be removed from the study at any time at the discretion of the clinician. Accordingly the clinician must complete the END OF STUDY form to reflect the date and reason for termination of the study for each patient. Any one of the following listed reasons may be applicable:

- 1) Patient has completed the 2nd year follow up evaluation.
- 2) Patient has completed the optional 3rd year follow-up evaluation
- 3) Failure of any of the Devices involved
- 4) Device related incident that led to deterioration of the patient's health and necessitating discontinuation
- 5) Patient death
- 6) Clinician's decision
- 7) Patient's decision
- 8) Sponsor decision for non-medical related reasons

11 Ethical considerations

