- **Clinician Baseline – Compulsory**, this form must be completed by the clinician with reference to each newly enrolled patient as it serves as registration of the patient at baseline evaluation. This is to ensure capture of the specific information related to technical details of the implanted device or devices and the external devices to be used, as well as any specific clinical technical details the patient does not have access to.
- **Annual Follow-up- Clinician (post implant: 1yr and 2yrs compulsory (and 3yrs optional))**. This is a general questionnaire that must be completed at an annual follow-up evaluation which coincides with routine annual clinic visit for the patient. This is to ensure capture of the specific information related to technical details of the implanted device or devices and the external

devices, and to reflect any changes that may have occurred over the preceding 12 months. Again it refers only to specific clinical technical details the patient does not have access to.

- **Product Specific procedures.**
- **End of study form** is also a compulsory form required to be completed by the clinician for each registered patient upon their departure from the registry either at the end of the prescribed set of evaluations, that is at 2 years or optionally 3 years post-implant or prematurely. A patient or clinician may choose to terminate participation in the registry prematurely at the individual wish of the patient or clinician or alternative following an event requiring removal of the patient from further review and data collection by the registry by default. The clinician is asked to record the reason for removal and date of exit from the study for each patient.
- **Unaided Hearing Threshold summaries.** The hearing threshold summary data recorded at baseline must reflect measurements performed prior to the implant surgery. Additionally, hearing thresholds measured immediately after surgery, in the period between surgery and before 1st switch-on or later) can be recorded at baseline evaluation. The evaluation form aims to capture a detailed summary of the pure tone hearing threshold levels that are routinely measured for the patient.
 1. **Pre-implanted hearing thresholds** routinely measured prior to the patients surgical procedure, for pure-tone stimuli via air and bone conduction in each ear for routinely measured frequencies between 125Hz and 8000 Hz) are required.

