### **1.3.3 Analysis Datasets**

#### **1.3.3.1 Intent-to-Treat**

Linear mixed-effects models provide unbiased estimates of effects even in the presence of missing data provided that the data may be assumed to be missing at random. All available data (to the last time point of interest – possibly 2 or 3 years due to limited follow-up beyond that time). The data will be examined for evidence of informed missingness.

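### Device failure or device-related deterioration may end a patient's data collection, so missing outcomes can depend on a poor result and mean benefit is probably slightly overstated

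*Protocol*

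**What the plan says.** - **Protocol 10.4** states that "the registered patient may be removed from the study at any time at the discretion of the clinician". Its list of possible reasons includes "Failure of any of the Devices involved" (reason 3) and "Device related incident that led to deterioration of the patient's health and necessitating discontinuation" (reason 4). Death, clinician's decision and patient's decision are separate entries (5, 6 and 7).
- **Protocol 6.1.3**, on the End of study form, also provides for exit after "an event requiring removal of the patient from further review and data collection by the registry by default". It does not name the events. The clinician records the reason and date of exit.
- **Protocol 1 (synopsis, Withdrawal)** says that a subject lacking the 1- or 2-year evaluation no longer counts for the longitudinal assessment.
- **Protocol 7.1** admits "First time implantees, post-lingually deafened, awaiting first switch-on". A patient whose record was closed and who was then re-implanted could not register again.
- **Protocol 10.3 and the synopsis** send incidents to post-market surveillance and promise to compare benefit with safety records.
- **SAP 1.3.3.1** relies on linear mixed models, unbiased "provided that the data may be assumed to be missing at random", and promises to look for informative missingness. SAP 1.3.4.1 and 1.3.7 describe patients with and without follow-up. SAP 4.1.1 requires paired pre- and post-implant scores.

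No section asks for HUI3 or SSQ after a device failure, or says how failure, explantation or re-implantation enters the benefit analysis.

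**The concern.** Reasons 3 and 4 let follow-up stop because of the device outcome itself. A patient who leaves this way before year 1 contributes a baseline score only. The patient then has no part in the paired HUI3 comparison or the logistic gain models of SAP section 4, and in the mixed model is represented by a score taken before the device was switched on. If such patients do worse than those who stay, the mean gain is too high. A device or configuration with more such exits loses more of its poor outcomes.

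The protocol intends these data for clinical, reimbursement, regulatory and marketing use (14.2), and its primary end-points include comparisons between device types and configurations (6.2.1). The benefit side of the promised benefit-safety comparison could omit patients who had the safety event.

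Continued collection looks feasible. The evaluations are mainly questionnaires completed alongside routine visits. Patients who receive a second implant stay in and are reclassified (7.1), and patients already enrolled may complete 2 years even if the sponsor closes the registry (section 15).

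**Working it through.** **1. Reproduce the plan's benefit estimate.** Inputs from SAP 4.1.2.1: mean paired HUI3 gain 0.1490534, t = 5.9659, df = 132 (133 pairs).
- SE = 0.1490534 / 5.9659 = 0.02498.
- 95% CI = 0.1490534 ± 1.978 × 0.02498 = 0.0996 to 0.1985; p = 2.10e-08.

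This agrees with the SAP. The estimate uses only patients with a 1-year score, so anyone removed before year 1 is outside it.

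**2. Overstatement of the mean.** Let f be the share of patients removed under reasons 3 or 4 before the visit. Then overstatement = f × (mean gain of retained − mean gain of removed). The retained mean is taken as 0.149. Both f and the gain of the removed are assumptions, because the documents give neither.

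| f (assumed) | Removed would have gained 0: f × 0.149 | Removed would have lost 0.149: f × 0.298 |
|---|---|---|
| 1% | 0.0015 | 0.0030 |
| 2% | 0.0030 | 0.0060 |
| 5% | 0.0075 | 0.0149 |
| 10% | 0.0149 | 0.0298 |

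The range is 0.0015 / 0.149 = 1% to 0.0298 / 0.149 = 20% of the observed gain. To reach the SAP's minimum important change of 0.03, f must be 0.03 / 0.149 = 20% (no gain) or 0.03 / 0.298 = 10% (loss of 0.149). The half-width of the confidence interval is (0.1985 − 0.0996) / 2 = 0.049.

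**3. Between devices.** If two devices had f = 1% and f = 5%, the spurious difference would be 0.04 × 0.149 = 0.006 to 0.04 × 0.298 = 0.012.

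**4. Bilateral against unilateral.** Assume a failure probability of 5% per device and independent failures. The chance of at least one failure is 1 − 0.95² = 9.75% for a bilateral user and 5% for a unilateral user.
- One failure costs the whole gain: 0.0975 × 0.149 = 0.0145 bilateral, against 0.05 × 0.149 = 0.0075 unilateral.
- One failure costs a bilateral user half the gain: 0.0975 × 0.149 / 2 = 0.0073, about the same as unilateral.

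**5. Does the SAP correct for it?** The mixed model removes the bias only if scores before exit, or covariates in the model, capture the failure. Before year 1 the only earlier score is the baseline. The checks in SAP 1.3.3.1, 1.3.4.1 and 1.3.7 are descriptive. The SAP specifies no sensitivity analysis for data not missing at random and does not mention the exit reason.

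**6. All-cause loss.** At the best-followed centre 161 − 117 = 44 patients (27%) have no 1-year data (SAP 4.1.1). The causes are not given, so none of this can be assigned to device failure.

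**The case against.** The strongest reply is that 10.4 is permissive. Removal is at the clinician's discretion, and reason 4 is limited to incidents "and necessitating discontinuation". Section 6.1.3 does not say that device failure is one of the events leading to removal by default. The annual clinician form asks about device changes over the past year, which fits continued follow-up. This stands. A reader might infer that every failure is cut off and that post-event data are wholly lost, but the documents do not support that. A failure after year 1 also leaves the year-1 score in place for the SAP's analyses.

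Incidents do reach surveillance, exit reasons are recorded, and the SAP will examine missingness. This also stands, but nothing says that surveillance collects HUI3 or SSQ after the event, and no planned analysis uses the exit reason. Discretion exercised after a poor outcome does not make the missingness ignorable, and it may vary by site.

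A reader might infer a larger bias for bilateral users because their chance of meeting the trigger is about double. Step 4 shows that this need not follow. Nor do the current SAP papers make the comparisons at risk: bilateral summaries were not possible (SAP 1.1), and the device-type paper uses baseline data only (SAP 2.2).

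Finally, benefit while the device works is a legitimate estimand when read beside safety data. The plan does not say that this is what it estimates.

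**Conclusion.** The concern holds in a limited form. The protocol permits data collection to end because of a poor device outcome, its two sections differ on whether removal is discretionary or by default, and the SAP's methods do not correct for the resulting missingness. Mean benefit is likely to be overstated, probably slightly: 0.0015 to 0.030 HUI3 units for an assumed 1% to 10% of exits, and below the 0.03 minimum important change unless roughly 10% to 20% of patients leave for these reasons. These figures rest on assumed exit shares and on removed patients having gained nothing or lost 0.149.

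Removal may differ by device and configuration. That bears on the protocol's hypotheses and between-group end-points (sections 5 and 6.2.1), not on the current SAP papers. It is worth changing because the remedy is cheap, not because a large bias has been shown.

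**What to change.** 1. **Protocol 10.4 and 6.1.3:** reconcile the two passages. State that reasons 3 and 4 are recorded as dated events and do not in themselves end data collection. Willing patients then continue the scheduled 1- and 2-year HUI3, SSQ and clinician forms, and are analysed under the originally registered device and configuration.
2. **Data already collected:** tabulate exits under reasons 3 to 5 by device type and configuration.
3. **SAP 1.3.2.3 and section 4:** add one sensitivity analysis that counts patients who left under reasons 3 or 4 as not achieving the gain at visits after their exit only. A patient who reached the gain at year 1 and left later keeps the year-1 result.

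The cost is a protocol wording change and one extra analysis of an existing field. Mean benefit may look slightly less favourable, and some patients will still decline further questionnaires. The change concerns data collection only, not clinical management.

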11.1 Declaration of Helsinki

The clinical investigation will be conducted according to the guidelines established in the latest update to the Declaration of Helsinki. Subjects will be free to withdraw from the observational study at any stage without prejudice to their subsequent routine clinical treatment.

11.2 Ethics Committee Approval/Opinion

As a non-interventional clinical observational study EC approval may not be required in some regions. Local or national exceptions may exist and must be determined and addressed ahead of participation by the clinician wishing to collaborate.

Any clinic wishing to publish their data is recommended to obtain Ethics Approval/Opinion for their participation in the Registry.

As a courtesy to all governing ECs, Cochlear will provide a current version of the Cochlear Registry Plan (in English unless otherwise requested), and the Patient Information Consent form (in the native language of patients).

As applicable the collaborating clinician at the investigator site is responsible for:

- Submitting the information package to the hospital EC prior to their participation in the Registry
- Any costs associated with gaining ethics approval
- Ensuring a copy of the EC opinion/approval letter to proceed is forwarded to Cochlear prior to initiation of the registry in their centre
- Responding to any queries raised by the local EC (requesting additional information from Cochlear as needed.)

11.3 Patient Informed Consent

The clinician is responsible for and must obtain written informed consent from each patient or their legal representative, prior to collecting any study data and formally enrolling them in the registry. This must occur after the patient is implanted when the decision for type and device configuration has already been taken independently to their decision to participate. Prior to obtaining their signature, verbal explanation and exchange must be provided to include:

- aims and objectives of study participation
- extent of the subject's involvement in terms of time, test intervals and tasks
- personal data privacy in printed material and electronic records
- their ability to cease their participation at any time during the course of the registry

The clinician is responsible to ensure that:

- all patients give written informed consent prior to enrolment in the registry through signing and dating the Patient Informed Consent form.
- a copy of the patient information sheet and consent form are given to the patient and the study details explained verbally.
- all signed patient informed consents are archived in the clinician's file at the centre/clinic, as per local requirements, and **at least for 5 years** after completion of the registry.

12 Data Reporting and Statistical Analysis

12.1 Statistical Method

Review of the study design was undertaken by an independent statistical consultant, [REDACTED] [REDACTED] Subsequently a proposal for the data analysis methods was made and is available as a separate report upon request (in English only).

In summary, based on the specified hypotheses assuming a 2-sided alpha error of 5%, (95% confidence interval) comparison of intra-subject performance outcomes rated via SSQ and HUI Mark III at preimplant to postimplant annual 1 and 2 years follow up intervals will require data for a minimum of **50** recipients with the same device to determine significant changes due to treatment effects.

13 Administrative Procedures of the Registry

13.1 Technical Requirements for online data entry

The minimum computer hardware and software equipment requirements must be available to enable data entry on line. Please verify and check that all of the below items are available for data entry at the clinic. Should the patient have elected to complete the forms online at their own discretion this also applies to any external computer accessed by the enrolled implanted recipient:

Hardware requirements:

- PC or Macintosh, Internet connection allowing normal and secured communications (HTTP, HTTPS)

Software requirements:

- Adobe Acrobat Reader, version min. 6.0
- Browser: Internet Explorer, Safari or Firefox.

13.2 Data Reporting

Evaluation case report forms to standardly gather general patient demographic data, and responses to the clinically standardised self-assessment scales, the SSQ and HUI MARK III, as well as audiometric data sheets (and product-specific measures), are provided as printable forms through the electronic user interface accessed via the allocated user password. The interface to the data sheets is designed for direct data-entry online with same time updates. Entered data is captured electronically into a central externally hosted e-platform developed, hosted and maintained by [REDACTED], as contracted database consultants for the company Cochlear, operating to ISO standards for data protection and data management. The project manager and select regional Cochlear staff will have access to view all raw data and data summaries. Clinics have ready access to all data entered related to their patients registered at their clinic via same time update summaries and through use of the system allocated confidential user password (delivered to each investigator by email). Subsequent automated email-reminders for patient reviews will also be provided through the e-platform as provided by the registering Clinician to alert for timely annual reviews of registered patients.

Specific instructions to complete the electronic evaluation forms shall be provided to the clinic investigator and other site personnel and registered patients online and reviewed during the initiation into the observational study onsite by Cochlear clinical staff.

Data entry at Baseline

Upon registration of the patient into the Observational study at baseline via the responsible clinician, the patient code will be automatically assigned via the platform according to the scheme outlined under the section entitled *Subject Identification and Confidentiality* of this protocol. During registration of the patient and completion of the *Clinician Baseline-Compulsory form*, the clinician and patient will agree upon which further assessments shall be included at baseline for the patient in question. The additional evaluation tools to select from include: Implant Recipient Baseline form, HUI Mark III and the SSQ and hearing threshold summaries and product specific evaluation measures.

Paper response options for the patient

Ideally if the paper option is preferred for the patient, at baseline and subsequent follow-ups, the clinician is advised to print-out the selected questionnaires prior to the evaluation interval, and to provide them to the patient for completion at the clinic, requesting return of completed questionnaires to the clinician before their departure from the clinic or upon subsequent return to the clinic. The clinician is responsible to review the forms in brief for completeness and to arrange online data entry for capture and storage of the data centrally.

Alternatively the patient may take the printed questionnaires home and return them to the clinician for data entry by post or at a later date. The clinician is responsible to review the forms in brief for completeness and to arrange online data entry.

Online response option for the patient

The patient providing consent to provide their email address through signature on the *Patient Informed Consent form*, and subsequently recorded online by the clinician on the *Clinician Baseline-Compulsory form* can provide responses on-line directly through use of a computer at home or in the clinic. The clinician can view the responses provided online by the patient and verify them at their discretion once the patient has submitted them online.

Follow-up evaluations

The clinician and patient may discuss and agree upon whether online data entry or paper entry for the patient is most desirable for follow-up evaluations.

If the patient has opted for online data entry, automated timely email reminders will notify the patient their responses for the next annual evaluation are due. Following no response by the patient a 2nd response will be sent to the patient. Following no response to the 2nd reminder by the patient, the clinician will be notified that an evaluation is due and no response to date. The clinician may review the situation with the patient at their discretion at the next appointment in the clinic. If the patient does respond to the first or 2nd reminder and enters new data, the e-platform will automatically notify the clinician that new data is available for the patient in question.

If the clinician and patient have opted for paper entry by the patient, the clinician will be reminded by email that a review of the patient in question is due at each annual review interval. If the clinician does not respond a second reminder is sent to the clinician. The clinician is ultimately responsible for re-entry of any data provided initially on paper by the registered patient at any interval.

